In addition, information from the EMRs of patients assigned to the nurse participants will be abstracted retrospectively under the Waiver of Consent after the patients have been transferred from the ICU. Patient factors will be used to help interpret the nurse participant data. However, concurrent patient data abstraction is not necessary for data analysis in this research project as there will be no intervention introduced that would impact the patient data. Further, patients in this ICU are usually unable to provide informed consent due to the presence of mechanical ventilation and continuous sedation.

IV. Inclusion/Exclusion Criteria

Inclusion criteria include English speaking, RN or LPN licensure.

Exclusion criteria include nurses helping to provide care but not having a patient assignment and nurse managers.

V. Number of Subjects

The study design is prospective, observational. The subject population is medical intensive care unit (ICU) nurses at University Hospital, MU Health Care. The anticipated number of subjects is 20. Normally, there are 10 nurses in each ICU per day shift (7:00 AM – 7:30 PM). During the data collection, the research team will monitor one designated medical ICU for 4 months (80 observation days).

VI. Study Procedures/Study Design

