Recruited nurses will receive two RTLS location tags prior to their shift from trained undergraduate industrial and manufacturing systems engineering (IMSE) students who will keep a log of the nurses' name and tag identification. The nurses will carry the tags for the duration of their shift and then return the tags to the students. While they carry the RTLS tags, IMSE students will stand at the corner of the nurse's station in each pod to record the nurses' activities and the time spent in these activities using a data collection form previously developed during earlier pilot work when IMSE students collected time-motion data regarding ICU nursing care activities. If any special events occur during the observation period, they will record a description of these events, which include but not be limited to unscheduled medical activities or admission of a new patient to the ICU from the Emergency Department (ED). The RTLS location tag distribution and nurse observation will occur four to five days per week until a total of 80 days of location and observation data is obtained. For each patient that is assigned to an observed ICU nurse, data will be extracted retrospectively from their EMR. The abstracted data will include: age, gender, hospital admitting diagnosis, medical ICU admitting diagnosis, past medical diagnoses, laboratory values occurring during, or 24 hours prior to observation time, neurological status, mean arterial pressures during observation time, intravenous medications administered during observation time, any diagnostic studies performed outside of the ICU during the observation time, and any in-room procedures performed during the observation time.

VII. Potential Risks

There is minimal risk to the participants in this study. There are no potential risks or discomfort for the participant as there will be no change in their work process. Methods to avoid inadvertent coercion in the recruitment process will be deployed.

VIII. Anticipated Benefits

Analyzing the ICU nurse's workflow can furnish an understanding of the causes of delayed and missed care delivery. The findings from this research will highlight opportunities to improve the workflow management design. Such information can guide future workflow management to reduce the ICU nurse's workload and the risk of delayed or missed care in the ICU resulting in improved patient outcomes.

IX. Compensation

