6. A log will be kept whereby the research team member distributing the location tags to the participants for the data collection session will enter the tag identification number; the co-investigator will enter the study code of the subject receiving the tag into the same log. In the event that there is an issue with the signal produced by the tag, the tag will be removed from service and substituted with another using the same log entry procedure. The removed tag will be inspected and tested by the PI and/or manufacturer. It will only be returned to service if the issue is resolved. Such events will be reported to NINR by the PI.
7. We will monitor the test on at least a daily basis looking for potential adverse events in compliance with existing The University Hospital policies and procedures. Adverse events may include:
 - a. Adverse patient outcomes attributable to the test
 - b. Statistically significant changes in patient outcomes
 - c. Any other unanticipated problems with the study
8. We will provide details to NINR and the IRB, including:
 - a. Details of the event
 - b. Any recommendations arising out of the study
 - c. Any actions taken as a result of a potential adverse event
9. As per the University of Missouri Health Sciences Institutional Review Board (IRB) Core Standard Operating Procedure for Event Reporting and the Standard Operating Procedure for Unanticipated Problems, the Principal Investigator will be responsible for:
 - a. Reporting to the University of Missouri Health Sciences IRB within 5 business days of the investigator becoming aware of unanticipated problems that meet all of the following criteria:
 - i. **unexpected** (in terms of nature, severity, or frequency) given (a) the research procedures that are described in the protocol-related documents, such as the IRB-

approved research protocol and informed consent document; and (b) the characteristics of the subject population being studied;

- ii. **related or possibly related** to participation in the research (possibly related means there is a reasonable possibility that the incident, experience, or outcome may have been caused by the procedures involved in the research); and
- iii. suggests that the research places subjects or others at a **greater risk of harm** (including physical, psychological, economic, or social harm) **than was previously known or recognized.**

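### Does listing significant outcome changes among events watched for daily conflict with abstracting patient data only after ICU transfer?

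*Protocol*

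**What the plan says.** Section X, item 7, opens with the commitment "We will monitor the test on at least a daily basis looking for potential adverse events", to be carried out in line with existing hospital policy. The list beneath it is introduced by "Adverse events may include" and has three entries: patient harm attributable to the test (7a), "Statistically significant changes in patient outcomes" (7b), and any other unanticipated problem (7c). Item 7b names no outcome, test, threshold, reference period or timetable.

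The patient data flow is described elsewhere. Section VI says: "For each patient that is assigned to an observed ICU nurse, data will be extracted retrospectively from their EMR". Section III is more specific on timing. Records of patients assigned to participating nurses "will be abstracted retrospectively under the Waiver of Consent after the patients have been transferred from the ICU". It adds that "concurrent patient data abstraction is not necessary for data analysis in this research project", on the ground that "there will be no intervention introduced that would impact the patient data".

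Section V states the design: "The study design is prospective, observational". It covers one medical ICU for 4 months, or 80 observation days. No control unit and no period before deployment is described.

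**The concern.** Taken at face value, 7b asks the team to look each day for something that needs assembled outcome data and a comparison. Staff can notice an attributable event (7a), an unexpected problem (7c) or an interfering tag (item 10b) on the day it happens. A statistically significant change cannot be noticed in that way. It has to be computed. On any given day the study's abstracted data exclude the patients then in the unit, and the protocol names nothing to compare them with. What is collected in real time (tag location, nurse activity, descriptions of special events) contains no patient outcome measure.

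Two things would be at stake. The IRB and NINR could be given a picture of closer outcome surveillance than the data flow supports. And if someone did run a test every day, chance findings could accumulate and be passed on under item 8.

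**Working it through.** The protocol gives no figure for 7b, so there is none to reproduce. The check is a comparison of the texts, followed by the only arithmetic that can be attached.

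**1. What is promised daily.** The daily commitment attaches to monitoring the test for potential adverse events. The list under it is permissive ("Adverse events may include"): it describes kinds of finding that would be treated as events. Nothing says that a significance test is run daily, or how often outcomes are reviewed.

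**2. What the data timing rules out.** Section III places abstraction after ICU transfer. That excludes same-day coverage, from study data, of patients still in the unit. It does not exclude review of outcomes as records come in. Section VI sets observation at four to five days a week until 80 days are reached, which is 80/5 = 16 to 80/4 = 20 weeks. Patients leave throughout that time, so abstracted data can accrue well before the end. A lag follows, but not an impossibility.

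**3. Whether another route is closed off.** Section III calls concurrent abstraction unnecessary for data analysis. It does not bar a separate safety route, and item 7 refers to hospital policies that are not part of this document. The protocol describes no such route in detail, but it does not contradict one. Item 5 (weekly review of collected data) and item 9c (a tracking system for trends) show that monitoring is not confined to a daily look, although neither supplies concurrent outcomes.

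**4. The missing reference.** That no comparator is named for a change is silence, not contradiction. The test, reference and threshold behind a significance statement are details that a protocol commonly leaves to a later plan.

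**5. What depends on 7b.** The objectives in Section I are to validate location data against manual observation (anticipated maximum error 5%), to correlate nursing activity with SOFA score, and to build a control chart for nursing processes. None uses 7b. On reporting, item 8 sends event details to NINR and the IRB. The 5-business-day IRB report in item 9 requires an event that is unexpected, related or possibly related, and suggestive of greater risk than was known. A chance p-value alone does not meet those criteria.

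**6. The false-signal arithmetic, and why it does not size the issue.** Suppose one test on each of 80 days at two-sided level α, with no true change.
- Independent daily tests: the chance of at least one signal is 1 − (1 − α)^80. At α = 0.05 this is 1 − 0.95^80 = 0.983. At α = 0.01 it is 1 − 0.99^80 = 0.552.
- Re-testing accumulating data: with S_k the sum of k independent standard normal increments, Z_k = S_k/√k, and a signal is any |Z_k| beyond the two-sided limit for k = 1 to 80. In 200,000 simulated null paths the proportion with a signal was 0.356 at α = 0.05 and 0.100 at α = 0.01.
- With few looks at accumulating data at 0.05: 0.083 for 2 looks and 0.126 for 4.

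The results therefore run from about 8% to 98%, depending wholly on an assumed level, number of looks and dependence between them. The independent case is extreme for a single ICU, where the same patients may be present on successive days. The figures also describe the consequence of daily testing, whereas the complaint is that daily testing cannot be done. They cannot serve as the size of this point.

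**The case for a change.** The best case for a change is that the conflict lies within one document and costs almost nothing to remove. An example in a safety plan is still something that the reader is told will be looked for. Testing for significance is itself data analysis, so the remark in Section III about concurrent data bears on 7b, and the reference to hospital policy supplies neither an outcome dataset nor a comparator. Section III also relies on the absence of any intervention that would affect patient data, while 7b watches for outcome changes. A later analysis plan could add a test, but it could not reconcile a daily watch with post-transfer abstraction.

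Part of this stands. Item 7b names neither a data source nor a review interval, and it reads awkwardly beside Section III. Study data cannot give same-day outcome coverage of current ICU patients. What does not stand is the step from there to a daily statistical procedure that the protocol commits to and cannot perform, because no such procedure is written. The suggested remedies also gain little. Deleting 7b would withdraw a safety undertaking without improving any estimate or protecting any patient. Scheduled reviews with a named comparator and an error limit would be a new surveillance design for a minimal-risk study, and a debatable one: a trend comparison within the study could not detect a shift that began at deployment.

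**Conclusion.** No change to the plan follows. There is a minor inconsistency of wording, confined to item 7b: an outcome-based event appears under a daily heading, while the only outcome data described arrive after ICU transfer. A sensible team would read 7b as applying to outcome data as they become available, and would carry out the daily watch through 7a, 7c and the tag and interference checks in items 6 and 10b, all of which can run daily.

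The effect on the study's estimates, precision and error rates is nil. No false-signal probability should be attached, because the protocol fixes no test, threshold or number of looks. The conclusion rests on reading the list in item 7 as permissive, which its lead-in supports, and on the study being observational with no intervention, as Sections III and V state. It would need revisiting only if daily significance testing of patient outcomes were in fact intended, in which case item 7 and Section III would have to be reconciled.
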